### 5.2 Recruitment

All patients undergoing cardiac surgery at enrolled centres will be invited to consent to the study.

### 5.3 Patients

Very low-risk patients are highly likely to go through cardiac surgery with few or no adverse events and thus easily achieve both survival and QoL benefits. This study will therefore focus on medium-risk and high-risk patients as being the ones more likely to yield useful information on failure to achieve QoL benefits. The best model for risk-stratifying cardiac surgical patients is EuroSCORE II and we aim to recruit patients whose risk is double the UK national average or higher (EuroSCORE II  $\geq 3\%$ ). This accounts for about a third of all cardiac surgery patients, approximately 13,000 patients a year.

Cardiac surgical patients (excluding, transcatheter aortic valve implantation or TAVI patients, emergency and salvage patients) will be recruited to this study nationally, and all cardiac centres will be invited to participate (we have already approached 5 key cardiac surgery centres and all have expressed enthusiastic support for the

study and willingness to participate). After initial recruitment, the management of patient follow-up will be conducted centrally from Royal Papworth Hospital.

#### **5.4 Identifying, informing and consenting patients**

Informed consent will be obtained prior to the participant undergoing any activities that are specifically for the purposes of the study. Patients will be provided with an information leaflet and consent for approved by the Research Ethics Committee. The procedure for informing and consenting patients will be the same in all centres and devised to accommodate local variations in the patient pathway.

Patients will be identified by a member of their clinical care team on acceptance to the surgical waiting list. Patients will be provided with a copy of the ethically approved patient information sheet and consent form. Patients will be allowed sufficient time to read, understand and ask questions regarding the study to be able to fully consider participation. Patients will have the opportunity to ask questions through the consent process and continuously throughout the study. The standard of care will not change whether or not a patient chooses to participate. Patients are free to withdraw at any time.

If patients do not possess the mental capacity to consent they will not be included in the trial due to the burden of having to complete monthly QoL questionnaires. Patients not fluent in English will be unable to participate as the scales are not validated for translation.

#### **5.5 Statistical analysis**

All statistical analyses and reporting will comply with CONSORT guidelines where possible.

Two single measures for QoL will be used for data analysis. The primary one is the mapping utility value of EQ-5D-5L; the other (as an alternative) is the SF-6D utility value mapped from SF12. An additional combine measure will be considered in case of considerable conflict in those two measures. This will be discussed formally in the statistical analysis plan.

Six outcomes will be used in all the analyses. The three primary outcomes will be defined as: (1) a continuous variable of a difference in the single measure of QoL between the baseline stage and a follow-up stage, this is a measure of the net QoL benefit ; (2) a binary variable of whether the post-surgery QoL has regained to the level at baseline; (3) a binary variable of whether the total sum of the first primary outcome over the follow-up time period where it is positive is larger to the period in which is negative, this is an indicator variable showing if a patient has achieved positive net QoL benefit. All the three primary outcomes will be based on EQ-5D-5L; the other three secondary outcomes derived from SF12 with the same definitions as (1), (2) and (3).

Three work packages will be designed to answer the aforementioned research questions of interest:

1. Perform descriptive statistics on (a) the first primary outcome at the stage immediately post-surgery; (b) the follow-up time (months) if the second primary outcome indicates the first occurrence of regaining (point estimate and confidence intervals); (c) the average trend of the first primary outcome over time; (d) the third primary outcome.
2. Perform inferential statistics on statistical testing to investigate the significance of variables in PANAS, LOT and patient frailty on the third primary outcome.

3. Develop a risk model on the third primary outcome by logistic regression or multilevel logistic regression.

In addition, the sensitivity analysis will be carried by doing the above three work packages replacing the primary outcomes with the three secondary outcomes based on SF12. The robustness of estimates and conclusions will be assessed. If a conflict exists, we may create a single measure of QoL by combining EQ-5D-5L and SF12 and do the same work packages.

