## 2 RATIONALE

In cardiac surgery, as in all branches of medicine, we treat patients so as to achieve two objectives:

[figure not shown]
- to improve quality of life (QoL)
- to improve survival

Deciding on an operation to improve survival is now easier due to sophisticated tools (EuroSCORE II & Tute) that measure and compare the risk to life of an operation with the risk to life from not having an operation. No such tool exists for QoL which is often the most important outcome for the patients.

Although some studies of cardiac surgery have included QoL as an outcome measure, no study has ever analysed the changes in QoL over time in the postoperative period and no study has ever analysed the relationship between individual patient and operation characteristics and the QoL outcome.

We know that most patients having heart surgery have symptoms (such as pain and breathlessness) which affect their QoL, and they submit to surgery in the hope of achieving relief from these symptoms and thus improving their QoL. We also know that, immediately after surgery, QoL is actually worse for all patients because postoperative pain, hospitalisation and functional limitation all have an impact. The normal scenario thereafter is that QoL then begins to improve, reaches the level it was before the operation and then hopefully exceeds it so that there will come a time when any QoL lost through surgery is 'paid back' by QoL gained. From that point onwards, the patient truly begins to benefit from having had the operation. The changes in QoL as a consequence of a typical major heart operation over time are graphically illustrated in the figure.

impact of a successful major open heart operation on quality of life

This is true for most patients, but not for all. A few will die from the operation. Some never regain the preoperative level of QoL, and some may not achieve a subsequent QoL improvement that matches or exceeds the QoL loss that occurs after the operation. Previous work indicates that between 8-19% of patients will experience a fall in QoL that does not recover.

When patients consent to major intervention, such as cardiac surgery, they need to know two things:

- 1) the risk to life of having an operation compared with the risk of not having an operation
- 2) the impact of an operation on QoL compared with the impact of not having an operation

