### **3 RESEARCH QUESTION/AIM(S)**

- 1) who will experience QoL net improvement and who will not within 12 month of surgery
- 2) what is the net gain/loss of QoL that an operation may produce and for which patients
- 3) how long before a patient having a heart operation begins to benefit in terms of QoL

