## 6. DATA COLLECTION

### 6.1 Methods

The data will be collected on to a web-based system designed and coordinated by the Trial Manager and Data Administrator at Royal Papworth Hospital. They will be responsible for training researchers to use the system and will conduct initiation visits.

QoL will be measured using the SF-12 and EQ-5D-3L at:

- baseline
- on hospital discharge
- at 1 month
- and every month for 12 months

Previous work has shown that, as a general rule, routine patients undergoing a routine cardiac operation are likely to have made a full recovery within 3 months if there are no complications and within 6 months if there are complications. To allow additional time for a return to preoperative QoL level, exceed it and achieve QoL benefits that reverse any QoL loss from surgery, QoL assessment will continue up to 12 months postoperatively, at which time patients who have not regained baseline QoL are unlikely to demonstrate any further significant QoL benefit.

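### Section 5.5 labels a single-stage change from baseline as net QoL benefit, and no continuous outcome measures the cumulative net gain or loss that aim 2 asks for

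*Protocol*

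**What the plan says.** Protocol section 5.5 lists three primary outcomes on the EQ-5D-5L utility and three secondary ones on SF12 with the same definitions.

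- Outcome (1) is continuous: "a difference in the single measure of QoL between the baseline stage and a follow-up stage, this is a measure of the net QoL benefit".
- Outcome (3) is binary. It asks "whether the total sum of the first primary outcome over the follow-up time period where it is positive is larger to the period in which" it is negative, and the text adds that "this is an indicator variable showing if a patient has achieved positive net QoL benefit".

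Section 2 (Rationale) describes the usual course as an early fall and then recovery, so that "there will come a time when any QoL lost through surgery is 'paid back' by QoL gained". It continues: "From that point onwards, the patient truly begins to benefit from having had the operation".

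Aim 2 in section 3 is "what is the net gain/loss of QoL that an operation may produce and for which patients". Section 2 lists the same question among those the risk model is to answer.

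Outcome (1) is used in two descriptive items of work package 1: its value immediately after surgery, item (a), and its average trend over time, item (c). Work package 2 tests predictors of outcome (3). Work package 3 is to "Develop a risk model on the third primary outcome by logistic regression or multilevel logistic regression".

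Section 6.1 schedules QoL at baseline, at discharge, at 1 month "and every month for 12 months", which gives 13 postoperative assessments.

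**The concern.** One term names two quantities. Outcome (1) is a change at one point in time. Outcome (3) is the sign of a balance accumulated over follow-up. A difference at one stage carries no information about what was lost at earlier stages, so it is not net in the sense of the Rationale, where earlier loss has to be repaid first.

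What is at stake is aim 2. It asks for an amount. Outcome (1) and its SF12 counterpart are the only continuous outcomes among the six, and their definition carries the net label. The cumulative amount whose sign gives outcome (3) is not itself an outcome. The study would therefore report who has a net benefit on one definition, while the only amount described as net is on another.

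**Working it through.** The plan states no figure for net benefit, so there is none to reproduce. The check sets the two definitions side by side on example profiles.

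**Inputs.** Let d be follow-up utility minus baseline utility at each of the 13 assessments in section 6.1. The profiles are assumptions, because the protocol gives no trajectories.

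**Formulas.**
- Outcome (1) at month 12 = d(12).
- Outcome (3) is positive if the sum of all d > 0 exceeds the absolute sum of all d < 0. The protocol's wording is loose, but a comparison of summed gain with summed loss is its most natural reading.

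**Profile 1.** Discharge −0.25; months 1 to 5: −0.20, −0.12, −0.06, −0.02, 0; months 6 to 12: +0.05 each.
- d(12) = +0.05.
- Gains: 7 × 0.05 = 0.35.
- Losses: 0.25 + 0.20 + 0.12 + 0.06 + 0.02 = 0.65.
- Balance: 0.35 − 0.65 = −0.30, so outcome (3) shows no net benefit.

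**Profile A.** Discharge −0.30; months 1 to 12: −0.30, −0.25, −0.20, −0.15, −0.10, −0.05, 0, 0.02, 0.04, 0.05, 0.05, 0.05.

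**Profile B.** Discharge −0.10; months 1 to 12: 0.05, 0.10, 0.15, 0.15, 0.15, 0.15, 0.10, 0.10, 0.05, 0, −0.02, −0.05.

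| Profile | Outcome (1), month 12 | Summed gain | Summed loss | Balance | Outcome (3) |
|---|---|---|---|---|---|
| 1 | +0.05 | 0.35 | 0.65 | −0.30 | no |
| A | +0.05 | 0.21 | 1.35 | −1.14 | no |
| B | −0.05 | 1.00 | 0.17 | +0.83 | yes |

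The signs disagree in both directions. Profiles 1 and A, an early loss followed by a modest late gain, have the shape that the Rationale calls normal.

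**Does time-weighting remove the disagreement?** Take profile 1 by the trapezoid rule, with discharge placed at 0.25 month (assumed).
- Discharge to month 1: 0.75 × (−0.225) = −0.169.
- Months 1 to 5: −0.16 − 0.09 − 0.04 − 0.01 = −0.30.
- Months 5 to 6: +0.025.
- Months 6 to 12: 6 × 0.05 = +0.30.
- Total: about −0.14 utility-months, still negative.

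**Illustration of frequency.** Trajectories d(t) = G − (G + D)·exp(−t/τ) were simulated for 400,000 patients per scenario. The mean drop D was 0.20 to 0.30, the mean long-run gain G was 0.06 to 0.08, and τ was 2 to 3 months, with variation between patients. In four scenarios, 11.7%, 17.9%, 26.9% and 31.4% of patients were positive at month 12 but not positive by area. These percentages depend wholly on the assumed curves and score the area, not the plain sum of visits.

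**The case against.** **Outcome (3) is built from outcome (1).** On this view the two are not rival definitions. Outcome (1) is the per-visit component and is called only a measure of net benefit, and either variable can be computed without its label. This is right as far as computation goes. It does not justify the label, since a component can have the opposite sign to the total.

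**Nothing planned goes wrong.** A reader might infer that the study will report a month-12 change as the net benefit, biased upwards, and that the calculator will then contradict the reported proportion. The protocol does not support this. No month-12 value is planned as the net benefit. Outcome (1) appears only in items 1(a) and 1(c), which show the early loss and the whole course. Work packages 2 and 3 use outcome (3). The direction is not fixed either, as profile B shows. This part of the objection stands in full.

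**The size is not evidence from the protocol.** This also stands. Section 6.1 cites full recovery within 3 months without complications and within 6 months with them. In the least favourable mean setting (D = 0.30, G = 0.06, τ = 3) the return to baseline comes at 3 × ln(0.36/0.06) = 5.4 months, close to the complicated limit. The upper percentage should not be read as expected.

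**A continuous cumulative value can be left to the statistical analysis plan.** That plan was not available for this review, and its silence cannot be assumed. However, section 5.5 fixes the six outcomes itself and attaches the net label to the wrong one. That is a statement in the protocol, not a detail left open.

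**Conclusion.** The point holds in a limited form. Section 5.5 applies net QoL benefit to a change at one stage and also to the cumulative balance behind outcome (3). The Rationale's account of benefit is cumulative, and the two quantities can differ in sign for the same patient. The tests, the risk model and the sample size do not change.

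The consequence is confined to aim 2. It asks how much is gained or lost on balance, no continuous cumulative outcome is defined, and the only continuous outcome described as net leaves earlier loss out. A binary model of outcome (3) cannot supply the amount.

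The sign disagreement follows by arithmetic and needs only the reading of outcome (3) as summed gain against summed loss. Its frequency is unknown. The 12% to 31% is an illustration under assumed trajectories. The correction is worth making before analysis because it lets the study answer its own second question at almost no cost.

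**What to change.** In section 5.5:

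1. Rename outcome (1) *change in QoL from baseline at each follow-up stage* and delete the clause that calls it a measure of net benefit. Its use in items 1(a) and 1(c) stays as planned.
2. Reserve *net QoL benefit* for the cumulative difference from baseline over follow-up to month 12, and define outcome (3) as whether that value is above zero.
3. Add the continuous cumulative value as the outcome that answers aim 2, with the SF12 version alongside it in the sensitivity analysis.

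An area under the curve in utility-months is a reasonable alternative to a plain sum of visits, because the interval from discharge to month 1 is unlikely to equal the others. It is not essential, but outcome (3) and the continuous value should use the same form.

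The cost is a change of wording and one derived variable. The visits are already scheduled, and the sum is already needed for outcome (3). The downside is that the reported net gain may be smaller than a late-visit change from baseline.

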## 5. RECRUITMENT AND SAMPLING

### 5.1 Sampling

The study will recruit a total of 8004 patients over two years and follow them up for 12 months. This sample size was derived as follows: according to Abah et al the percentage of people expected not to regain QoL after heart surgery and after 12 months is between 8-19%. Additionally, there is a 4% predicted mortality rate for heart surgery in the UK in the higher risk population which is the subject of this study. Therefore, a conservative estimate is that 12% of patients in this study would not regain QoL. Assuming the 12% rate as a reference value, with a minimum of 6670 patients we would be powered to produce a predictor tool with a sensitivity of at least 0.75 (or true positive rate to identify those patients that do not regain QoL after surgery) and a 3% error ( $0.75 \pm 0.03$ ) at the 95% confidence level. Anticipating a non-response rate of 20%, we will recruit an additional 1334 patients to compensate for this, giving a total of 8004. Based on the above, the study will estimate the proportion of patients who do not regain QoL after 12 months with a 95% confidence of  $\pm 0.7\%$  (for a rate of 8%) and  $\pm 0.8\%$  (for a rate of 12%) with 6670 patients.

Recruitment and drop-out rates will be continuously monitored by the trial steering committee (TSC). To recruit 8004 patients, we plan to approach all 36 cardiac centres in the UK. Assuming only 30 centres take part (a feasible number based on our NIHR ETTAA study) and a two-year recruitment period, there will be 20000 patients with a EuroSCORE II  $\geq 3$  who would be eligible for the study over two years. Our sample size calculation requires that 40% of the eligible patients consent over the two-year period. This translates into no more than 134 patients per centre per year, a recruitment target that is conservatively achievable. Based on our original approach to 5 centres, the recruitment rate will average 192 patients per centre per year, so that the required 134 patients per centre per year is achievable and will be carefully monitored by the project management team and the TSC as described in the section 9.4 of this protocol.

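### Section 5.1 counts deaths as failures, but the outcomes in 5.5 have no rule for death, so a death can go unscored or be scored as net benefit

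*Protocol*

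**What the plan says.** **Sizing (Protocol, 5.1 Sampling).** From a cited review, "the percentage of people expected not to regain QoL after heart surgery and after 12 months is between 8-19" per cent. The next sentence is "Additionally, there is a 4% predicted mortality rate for heart surgery in the UK in the higher risk population", and the conclusion is "Therefore, a conservative estimate is that 12% of patients in this study would not regain QoL". On that rate, "with a minimum of 6670 patients we would be powered to produce a predictor tool" "with a sensitivity of at least 0.75", within 0.03, "at the 95% confidence level".

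**Outcomes (Protocol, 5.5 Statistical analysis).** There are three primary outcomes, all based on the EQ-5D utility:
- Outcome 1 is the difference between baseline and a follow-up stage.
- Outcome 2 is whether QoL has returned to its baseline level.
- Outcome 3 is whether "the total sum of the first primary outcome over the follow-up time period where it is positive is larger" than the sum over the period where it is negative.

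The SF-12 outcomes repeat these definitions. Work package 1(b) describes the time to the first regaining. Work packages 2 and 3, which include the risk model, use outcome 3.

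**Data (Protocol, 6.1, 6.3 and Appendix 2).** QoL comes from questionnaires at baseline, at discharge and monthly to 12 months, and patients complete the follow-up ones themselves. The schedule of procedures lists no vital-status item after discharge.

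**The concern.** The two sections treat death differently. In 5.1 a death is one of the patients who fail to regain QoL. In 5.5 no definition assigns a value or a category to a patient who has died, and outcome 3 can be computed from whatever scores exist before death.

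Outcome 3 is the one that is modelled, and the calculator built on it is meant to inform consent to higher-risk surgery. If the definitions are applied as written, some deaths leave the model and others may be recorded on the benefit side. The number of failures would then also differ from the number on which 6670 rests.

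**Working it through.** **1. Reproduce 6670.** Inputs from 5.1: sensitivity 0.75, half-width 0.03, 95% confidence (z = 1.96), failure rate 12%.

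N = z² × Se × (1 − Se) / (d² × rate) = 1.96² × 0.75 × 0.25 / (0.03² × 0.12) ≈ 6669.2, rounded up to 6670. The stated figure reproduces, and it needs the full 12%.

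**2. Share of deaths at the lower-end rate.** Reading 12% as 8% + 4%:
- expected failures: 0.12 × 6670 = 800
- deaths among them: 0.04 × 6670 = 267, or 4/12 = one third
- other failures: 0.08 × 6670 = 534

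**3. Precision of sensitivity if no death counts as a failure.** Half-width = 1.96 × √(0.1875 / number of failures), with 6670 patients.

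| Non-death failure rate | Failures | Half-width |
|---|---|---|
| 8% | 534 | ±3.7 points |
| 12% | 800 | ±3.0 points |
| 19% | 1267 | ±2.4 points |

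At 8%, restoring ±3.0 would take about 10,004 patients including those who die. Equivalently, it takes 9,604 survivors at 8/96 = 8.33%, since 9,604 / 0.96 = 10,004.

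**4. Failure proportion.** If the 8% is of all patients, survivors show 8/96 = 8.3% against 12%. The gap is 3.7 points, about 4.6 times the ±0.8% stated in 5.1 (3.7 / 0.8). If the 8% is of survivors, the contrast is 8% against 0.08 × 0.96 + 0.04 = 11.7%, again 3.7 points.

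**5. Outcome 3 as written.**
- *Death before the first post-operative questionnaire:* there are no differences to sum, so there is no value.
- *Later death, with assumed differences:* discharge −0.20, then months 1 to 4 at −0.10, +0.10, +0.15 and +0.20, then death. The positive sum is 0.45 and the negative sum 0.30, so the patient is scored as net benefit.
- *Same patient with utility 0 after death and an assumed baseline of 0.60:* the negative sum becomes 0.30 + 8 × 0.60 = 5.10, so the patient is scored as no benefit.

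The result for this patient therefore depends on a rule that 5.5 does not contain.

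**6. Outcome 2 and work package 1(b).** An in-hospital death reads naturally as not regained. A patient who regains baseline and then dies has already had a first regaining and would count as regained.

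**The case against.** *This is silence, and the SAP may supply the rule.* Section 5.5 does not restrict the analysis to survivors or complete cases, and the handling of death in a utility score often sits in the SAP, which was not available here. That limits the point: a reader might infer that the plan excludes deaths, and it does not say so. But the outcome definitions are stated in the protocol, the reference to the SAP in 5.5 comes with the choice and possible combination of QoL measures, and the definitions as written do not match the failures counted in 5.1.

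*The sizing concerns outcome 2, while the rule quoted concerns outcome 3.* This stands. Section 5.1 gives no event rate for outcome 3, so the figures in steps 2 to 4 describe failure to regain QoL and are not shown for the modelled outcome.

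*The study is not necessarily too small.* This also stands. A reader might infer that the event count is missed, or that about 10,004 patients are required. Both hold only at the 8% end of the 8–19% range and only if no death counts as a failure.

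*Survival is handled elsewhere.* Section 2 treats survival and QoL as separate objectives and points to existing tools for mortality risk. A survivors-only QoL model is legitimate if declared, but then deaths do not belong in the 12%.

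**Conclusion.** The inconsistency is real and lies within the protocol: deaths are failures in the sample size and have no defined place in the outcomes. Applied literally, outcome 3 leaves a death before any post-operative questionnaire without a value and can score a later death as net benefit.

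At the lower-end rate, deaths are 267 of 800 expected failures. If none counts, sensitivity is estimated to about ±3.7 points instead of ±3.0, and the failure proportion is about 8.3% of survivors instead of 12%. This rests on reading 12% as 8% + 4%, a sum that 5.1 implies but does not write out. At a non-death failure rate of 12% or more, ±3.0 is still met.

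A reader might go further and infer that predictors of death will look favourable in the model. The documents do not support that. They do not give the timing of deaths, so the split between unscored and misclassified deaths is unknown, and no direction of bias can be stated.

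**What to change.** In 5.5, state that:
- death within 12 months is classed as not regained at 12 months in outcome 2 and as no net benefit in outcome 3, whatever the earlier scores or the baseline utility;
- death is a competing event for the time to first regaining in work package 1(b);
- for outcome 1, utility is set to 0 from death in one analysis, with a survivors-only version reported as secondary.

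The explicit classes are needed because utility 0 alone is not enough. It does not undo a regaining before death, it can leave a late death with a positive sum, and it turns death into a gain when baseline utility is below 0.

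Record the date of death up to 12 months, so that a death is not taken for non-response.

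With this rule the 12% and the 6670 in 5.1 stand. If the sponsor intends a survivors-only model instead, say so in 5.5 and restate the 12% and the ±3% precision in 5.1 without deaths.

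The cost is one rule in the protocol or SAP and a vital-status check for patients who stop responding.

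### Primary outcome 3 sums scores without time weights, so who is classed as having net benefit depends on how the discharge score is counted

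*Protocol*

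**What the plan says.** Section 5.5 of the protocol builds primary outcome 3 from primary outcome 1, which is "a difference in the single measure of QoL between the baseline stage and a follow-up stage". Outcome 3 then asks "whether the total sum of the first primary outcome over the follow-up time period where it is positive is larger" than the corresponding total where it is negative, and adds: "this is an indicator variable showing if a patient has achieved positive net QoL benefit". No interval weight, integral or area under the curve is named. The SF-12 counterpart takes the same definition.

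Section 6.1 schedules quality-of-life measurement at baseline, "on hospital discharge", at 1 month "and every month for 12 months". Appendix 2 agrees. That makes 13 postoperative assessments, the first on no fixed day.

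Section 5.5, work package 1(a), describes "the first primary outcome at the stage immediately post-surgery". Discharge is the only scheduled assessment before month 1, so on a plain reading the discharge score is one value of outcome 1 and one term of the sum.

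Outcome 3 is the dependent variable of work package 2 (tests of PANAS, LOT and frailty) and work package 3 (the risk model).

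**The concern.** Section 2 describes a fall in quality of life straight after surgery, a recovery, and a time at which the loss has been made good by later gain. That quantity is cumulative over time. An unweighted sum approximates it only when assessments are equally spaced, and the interval from operation to discharge to month 1 is not.

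Section 2 also says that quality of life is worse for all patients immediately after surgery, so the wrongly weighted term will tend to be negative. Its true time span depends on length of stay, which may itself be related to frailty and operative risk, the characteristics that the study wants to relate to the outcome. A patient discharged close to one month would have two full-weight scores for much the same period.

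At stake is the binary outcome on which the risk model and the calculator rest. The sensitivity analysis on SF-12 repeats the same definition and so cannot reveal the problem.

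**Working it through.** **The plan's own figures.** The protocol gives none for outcome 3. Its sample size in Section 5.1 reproduces: 1.96² × 0.75 × 0.25 / 0.03² = 800.3, and 800.3 / 0.12 = 6669 (stated 6670). That figure concerns not regaining quality of life and does not bear on this point.

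**The rule.** Positive differences outweighing negative ones is the same as the plain total of all differences being above zero. Each assessment therefore has weight 1.

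**Weights in a trapezoidal area.** Assumed: discharge at day 7 to 14, a month of 30.4 days, so t = 0.230 to 0.461 month.

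| Score | Sum | Area from surgery, discharge value carried back | Area from discharge |
|---|---|---|---|
| Discharge | 1 | t + (1 − t)/2 = 0.615 to 0.730 | (1 − t)/2 = 0.385 to 0.270 |
| Month 1 | 1 | (1 − t)/2 + 0.5 = 0.885 to 0.770 | same |
| Months 2 to 11 | 1 | 1 | 1 |
| Month 12 | 1 | 0.5 | 0.5 |

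**One assumed recovery profile.** Differences of −0.40 at discharge, −0.20 at month 1, −0.10 at month 2, 0 at month 3, and a constant gain g at months 4 to 12.

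- Sum with discharge: −0.70 + 9g, positive when g > 0.078.
- Sum of months 1 to 12 only: −0.30 + 9g, positive when g > 0.033.
- Area from surgery, day 7: −0.40 × 0.615 − 0.20 × 0.885 − 0.10 + 8.5g = −0.523 + 8.5g, positive when g > 0.062.
- Area from surgery, day 14: −0.40 × 0.730 − 0.20 × 0.770 − 0.10 + 8.5g = −0.546 + 8.5g, positive when g > 0.064.
- Area from discharge: −0.431 + 8.5g (day 7) or −0.362 + 8.5g (day 14), positive when g > 0.051 or 0.043.

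At g = 0.07 the sum with discharge is −0.07 (no benefit), while the area from surgery is +0.07 at day 7 and +0.05 at day 14 (benefit). At g = 0.05 the sum without discharge is +0.15 (benefit), while the area from surgery is −0.10 and −0.12 (no benefit). At day 7 the sum with discharge overstates the loss by 0.70 − 0.523 = 0.177, of which the discharge score accounts for 0.40 × (1 − 0.615) = 0.154.

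**Simulation, all inputs assumed.** 200,000 patients per scenario, complete data, discharge at day 7. Lasting gain is normal. The discharge difference has SD 0.15. Recovery is exponential at 0.4 to 1.2 per month, with score noise of SD 0.08. The sum with discharge is compared with the area from surgery.

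| Lasting gain, mean (SD) | Mean at discharge | No benefit by area | Changed class by the sum | Of these, benefit to none |
|---|---|---|---|---|
| 0.12 (0.10) | −0.3 | 25.2% | 3.4% | 3.4 points |
| 0.15 (0.12) | −0.2 | 17.3% | 1.8% | 1.7 points |
| 0.10 (0.10) | −0.2 | 26.3% | 2.5% | 2.4 points |
| 0.20 (0.12) | −0.3 | 11.5% | 1.8% | 1.8 points |

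**The case against.** Three objections carry weight.

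First, the reference to the follow-up period in the definition could loosely mean an area. If so, one sentence settles it, but the text names a sum of differences and no area.

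Second, discharge may not belong to the sum at all. Sections 6.2 and 6.3 separate baseline and discharge data from follow-up questionnaires, and Appendix 2 gives discharge and follow-up quality of life separate rows. With monthly scores only, spacing is equal. The ambiguity is real, but this reading does not rescue the definition: it drops the early loss that Section 2 wants set against later gain, and in the profile above it lowers the threshold to 0.033.

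Third, the size rests on assumptions, and the start point of the area matters about as much as the weighting (0.043 to 0.051 from discharge, 0.062 to 0.064 from surgery). That stands, and the fix must therefore state the start point.

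A reader might also infer more than the documents support:

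- *That a missed month counts as zero and so favours benefit.* The protocol does not say whether the sum uses available, complete or imputed scores, and that rule may be in the analysis plan, which is not at hand. The allowance in Section 5.1 ("Anticipating a non-response rate of 20" per cent) serves to enlarge recruitment and is not stated to be a rate of missed questionnaires. Missed good months would also pull the other way.
- *That the shift exceeds the planned precision of ±0.8%.* That figure is for the proportion not regaining quality of life, which is not outcome 3.
- *That outcome 3 is the only outcome to be modelled.* Section 11 also plans models for the extent of benefit or loss.
- *That about 5% of patients are misclassified.* A scenario with a mean lasting change of 0.03 (SD 0.08) gives 5.4%, but it leaves 57.5% without net benefit by area. That sits badly with Section 2, which expects overall benefit and a minority who lose.

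**Conclusion.** The point holds as a fault in the definition. Outcome 3 is worded as an unweighted sum over an unequally spaced schedule, and neither treatment of discharge gives the cumulative quantity that the protocol wants. With discharge included, borderline patients move towards no net benefit; with it excluded, they move towards benefit.

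The size cannot be derived from the protocol. Under the assumed length of stay, recovery shapes and spread of gains, with complete data and discharge included, about 2 to 3% of patients change class, nearly all from benefit to no benefit. That is modest, but it is systematic, it falls on the dependent variable of work packages 2 and 3, and it may vary with length of stay. The change should be made before analysis; the point does not call the design into question.

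**What to change.** Define outcome 3, and its SF-12 counterpart, as the sign of the time-weighted (trapezoidal) area of the utility difference from baseline, from surgery to month 12, on actual assessment dates. State that the discharge score is included. Utility is not measured between surgery and discharge, so fix the value used there, for example the discharge value carried back. Add a sensitivity analysis in which the area starts at discharge. Leave the handling of missed questionnaires to the statistical analysis plan, which should apply it before the area is taken.

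The cost is one rewritten definition and a little more analysis work, with no change to the assessment schedule. Completion dates must be available for every form: Section 6.3 describes an audit trail for electronic entry, so dates on paper questionnaires need to be recorded as well.
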